# 3. Study Procedures:

# **Overview and design**

We plan to recruit at least 24 English-speaking participants aged 18-85 years with a history of chronic TBI (> 1 year since injury), all of whom have problems with cognition. Participants will be randomized into an active HD-tDCS condition or a sham condition in order to assess the efficacy of HD-tDCS on improving cognition. The proposed study will measure response to HD-tDCS treatment over the preSMA region when compared to sham. Participants will receive two phases of 10 sessions of active stimulation (1 mA anodal HD-tDCS targeting preSMA for 20 min) or sham across 2 weeks. All participants will be blinded to their condition. EEG and neuropsychological tasks will be completed at

baseline, immediate follow-up after session 10, and a 2-month follow-up. Those participants randomized into the active or sham group will have the opportunity to return after 2 months and receive sham (if active first) or active (if sham first) treatment and will undergo the EEG and neuropsychological tests again immediately following the last HD-tDCS session and at a 2-month follow-up. With this design, we expect a 15% attrition rate and plan on enrolling ~30 adults to achieve our completed sample of 24.

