# Sample size justification

Pre-study power analyses were conducted for the most power intensive phase of the study (Phase 1), using a clinically relevant effect size (Cohen's d = 1.20) derived from our prior studies. Holding 1- $\beta$ =0.8, and a=0.05, a sample size of 20 would provide sufficient power to identify true interaction effects (treatment \* time) across all neuropsychological outcome measures in the magnitude of f=0.27 (Cohen's d ≈ 0.54). Given that both our and other's research without intervention suggests that effect sizes tend to be larger in EEG compared to neuropsychological outcomes. We expect the effect size of EEG outcomes to be at least equivalent to neuropsychological outcomes. Still, we will perform an interim power analysis based on EEG data once half of the targeted recruitment is reached to ensure adequate statistical power. As the proposed sample size provides sufficient power to detect moderate effects for all outcomes, our study is well powered.

Below is a table summarizing the study visits followed by a detailed description of the procedures for each visit. It is a two Phase study. In Phase 1, participants will be randomized to active stimulation (1 mA anodal HD-tDCS targeting preSMA for 20 min) or sham and complete 13 visits. Then in Phase 2, participants who have been in the active group in Phase 1 will be invited to receive the active stimulation condition, and those who have been in the sham group in Phase 1 will be invited to receive the sham stimulation condition. Either way would involve 11 additional visits in the study.

TABLE 1. SUMMARY OF VISITS		
Phase 1	PROCEDURES	TIME
Visit 1	Pre-testing neuropsychological assessment/semantic EEG	3 hours
Visit 2	Pre-testing MRI scan	1 hour
Visits 3-11	HD-tDCS active or sham stimulation	30 minutes
Visit 12	HD-tDCS active or sham stimulation and post-testing neuropsychological assessment/semantic EEG	3 hours
Visit 13	8-week follow-up assessments/semantic EEG	3 hours
Phase 2		
Visits 14-22	HD-tDCS sham or active stimulation	30 minutes
Visit 23	HD-tDCS active stimulation and post-testing neuropsychological assessment/ semantic EEG	3 hours
Visit 24	8-week follow-up assessments/semantic EEG	3 hours

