Transcranial Direct Current Stimulation (tDCS) is a non-invasive technique that requires the placement of several sensors (metal electrodes) on a special cap and saline gel on the participant's head. Very low levels of constant electrical current are delivered to specifically targeted areas of the brain via these electrodes. Contact quality and impedance levels (<10 kOhms) will be verified before each session. The same preparation is used for both active and sham conditions. After each session, subjects will be administered a standard post-treatment symptom questionnaire (e.g., assessing for skin irritation). Daily treatment lasting for 20 minutes (total of about 30-40 minutes including preparation) will be administered over 2 weeks (5 daily sessions each week), as scheduling allows. Session scheduling will depend on participant availability and availability in the lab. All treatment sessions will be held in [name] lab at UTDallas.

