Assessment sessions, including the neuropsychological test battery and the Semantic Selection and Semantic Object Retrieval EEG tasks, will be completed at baseline, after intervention session 10, and at 2-month follow-up assessments. Each assessment session lasts approximately 3 hours. Specifically, the neuropsychological testing will take approximately 1 hour and will assess skills in the areas of word retrieval, episodic memory, processing speed, executive functions, and visuospatial organization. Participants will be asked to complete a few guestionnaires about emotional state and cognitive performance as well as completing computer tasks. These tests might be completed through in-person or remote online interviews. In addition, MRI scan will be obtained at baseline that include structural imaging and takes place at UTSW advanced imaging research center. Participants will also undergo event-related electroencephalography (EEG). The EEG procedure is a non-invasive technique that requires the placement of 64 sensors (metal electrodes) and saline gel on the scalp. The electrodes will record brain electrical activity while participants sit quietly in a chair and perform computer-based tasks. During the event-related EEG participants will be asked to react to visual stimuli shown on a screen using a button box. The EEG procedure will take place at the UT Dallas Callier Center for Communication Disorders, or Research and Operations Center West, both of which are in the laboratory of [name]. The EEG procedure takes nearly 2 hours.

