# 7. Criteria for Exclusion of Subjects:

- Lifetime major neurologic syndromes (e.g., stroke, epilepsy, brain tumor)
- Lifetime major cardiovascular conditions (e.g., heart attack, heart failure)
- Current substance use disorder
- Lifetime major psychiatric disorders (e.g., schizophrenia, bipolar disorder)
- Current sensory or physical impairment that interferes with testing
- Implanted device such as a pace maker or other neuro-stimulator
- Has metal fragments in head
- Pregnancy

If a medical condition becomes apparent during the evaluation or follow-up that indicates an increased risk then the subject's involvement in the study will be discontinued.

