#### Risks from the HD-tDCS:

Overall, HD-tDCS has been found to be a safe, well tolerated investigational device as well as a treatment tool when used within the standard parameters. No serious adverse advents caused by HD-tDCS have been reported in the scientific literature. The research team will stop the procedure immediately if the subject chooses. Common side effects include:

- Possible skin sensations, such as tingling, itching, and burning sensations at the site of electrodes, that resolves when stimulation is finished. When experienced, the majority of these are mild in nature with fewer than 4% of individuals describing the sensations as intense.
- Very rarely, temporary skin irritation may occur under the electrode. This creates a darkening of the skin, which normalizes after a week and heals. The size of such is a few millimeters.

To minimize risk, all subjects will be monitored with one-on-one direct supervision during HD-tDCS sessions. If subjects experience discomfort more than the mild tingling or itching expected during HD-tDCS and are unable to continue, the HD-tDCS session will be immediately terminated.

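### The plan provides no immediate post-test for participants who stop stimulation early, and a medical discontinuation ends outcome assessment along with stimulation

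*Combined protocol and SAP*

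**What the plan says.** Section 3 ties the first post-treatment outcome to the tenth session twice. Overview and design lists the assessment times as "baseline, immediate follow-up after session 10, and a 2-month follow-up". The later description of the assessment sessions says they "will be completed at baseline, after intervention session 10, and at 2-month follow-up assessments". Table 1 puts this into visits: Visit 12 is "HD-tDCS active or sham stimulation and post-testing neuropsychological assessment/semantic EEG", and Visit 23 is its Phase 2 counterpart. No other visit yields the immediate outcome. The 8-week assessment has its own visits without stimulation (Visits 13 and 24).

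Two rules cover stopping. Section 7 applies when a medical condition comes to light during evaluation or follow-up and "indicates an increased risk then the subject's involvement in the study will be discontinued". In Section 10, under Risks from the HD-tDCS, participants with more than the expected discomfort who are "unable to continue, the HD-tDCS session will be immediately terminated". That rule does not mention later sessions or assessments.

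Section 14 expects attrition to leave gaps at some assessment times but not all, and fits a linear mixed model by likelihood methods. It names no analysis population and describes no sensitivity analysis for missing data.

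**The concern.** Stopping stimulation and stopping measurement are separate events, and the plan does not keep them apart. A participant who leaves under the Section 7 rule before Visit 12 has no post-treatment value at all, although Risks from EEG lists only tiredness and emotional discomfort for that procedure. A participant who stops for discomfort or by choice has no visit at which the immediate outcome would be taken. Staff would have to decide case by case whether to recall them.

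At stake is whether the result describes everyone randomized. If those who stop would have done differently from those who continue, in a way that baseline does not predict, the estimate is shifted and the planned model cannot show it. Some of these outcomes could have been collected. Once the time for the assessment has passed, they cannot be recovered.

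**Working it through.** **The plan's own figure.** Overview and design gives 24 completers, 15% attrition and about 30 enrolled.
- 24 / (1 - 0.15) = 28.2, rounded up to 29, which agrees with about 30.
- Losses allowed for: 30 x 0.15 = 4.5 at the stated rate, and 30 - 24 = 6 (20%) at the stated enrolment. That is about 4 to 6 people.
- The rate is stated after both phases are described, so it appears to cover the whole study. Nothing says how many losses would fall before Visit 12.

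**What each kind of early stop leaves behind.**
- Discontinued under Section 7 before Visit 12: baseline only. All four post-baseline occasions (two times in each of two phases) are lost.
- Stopped for discomfort or by choice in Phase 1 before session 10: no visit for the immediate post-test. Visit 13 is not made conditional on session 10, but Section 14 counts its eight weeks from treatment, and no starting point is given for someone who stopped partway.
- Stopped in Phase 2: the Phase 1 post-treatment data are kept.

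**What the model does with a baseline-only participant.** The tested contrast in Section 14 is (μ1j + d1j)/2 - (μ2j + d2j)/2, where each term is a mean change from baseline. A participant with a baseline value alone informs the common baseline mean μ0 and adds almost nothing to these terms.

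**Possible shift (assumed inputs).** The documents give no outcomes for early stoppers. Let p be the share of one arm lost and g the amount, in SD, by which their outcome is worse than that of the others and not predicted by baseline. If M is the mean of those observed, the mean of the whole arm is (1 - p)M + p(M - g) = M - pg. The observed mean is therefore too high by p x g.

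| p | g = 0.25 | g = 0.5 | g = 1.0 |
|---|---|---|---|
| 0.15 | 0.0375 | 0.075 | 0.15 |
| 0.20 | 0.05 | 0.10 | 0.20 |

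The range is about 0.04 to 0.20 SD for one arm's mean. The contrast gives each phase a weight of one half, so if only Phase 1 data are lost it moves by pg/2: 0.0375/2 = 0.019 to 0.20/2 = 0.10 SD. For scale, Sample size justification gives d of about 0.54. The arm-mean shift is 0.0375/0.54 = 7% to 0.20/0.54 = 37% of that, and the contrast shift is 0.019/0.54 = 3.5% to 0.10/0.54 = 19%.

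For a participant who misses Phase 2 as well, the shift also depends on the missing Phase 2 outcomes. No figure in the documents bears on those, so it is not computed.

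**The case against.** Several points on the other side stand.

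- A reader might infer that everyone who stops early has no post-treatment data. The documents do not support that. Only the Section 7 rule ends involvement. The discomfort rule ends a session, the 8-week visit does not depend on session 10, and Phase 2 stoppers keep their Phase 1 results. For discomfort and voluntary stops, follow-up is unspecified rather than excluded.
- A reader might also infer that the comparison becomes one of completers. Section 14 defines no completer set, keeps partial data and indexes condition by random assignment. The difficulty is confined to people with little or no post-baseline data.
- More stopping on active current is an assumption. Risks from the HD-tDCS calls the sensations mostly mild, with fewer than 4% of people finding them intense, and no sham rate is given. That is not a stopping rate, but used as a rough p it gives 0.04 x 0.25 = 0.01 to 0.04 x 1.0 = 0.04 SD. The Section 7 rule concerns medical conditions, and the documents give no reason to expect those to differ by arm.
- Flexible timing might seem to be part of the same problem, since "Session scheduling will depend on participant availability and availability in the lab". Slippage loses no outcome. Testing such people on a calendar date would catch them mid-course, against an endpoint defined as following the intervention.

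The objection does not remove the gap. No text says that early stoppers will be assessed, and the likelihood model cannot supply a change from baseline that was never measured.

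**Conclusion.** The point holds in a limited form. As written, the plan gives up outcome data it could still collect: all post-treatment data for anyone discontinued under Section 7 before Visit 12, and the scheduled immediate post-test for others who stop early in Phase 1. For these people the result rests on a missing-at-random assumption that the plan does not test.

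The size is unknown. The range of about 0.04 to 0.20 SD for one arm's mean assumes that 15-20% of that arm is lost, that the losses fall in that arm only, and that outcomes are 0.25-1.0 SD worse than baseline would predict. In the phase-averaged contrast it is about half that if only Phase 1 data are lost. It is nil if losses are balanced and unrelated to outcome, though the data are still lost. No new sample size follows.

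**What to change.** - In the Section 3 description of the assessment sessions and in Table 1, state that the post-test and the 8-week assessment are sought for every randomized participant. Those still receiving sessions, including those whose sessions have slipped, are tested after session 10. Those who have permanently stopped stimulation are tested at the time session 10 would have occurred, within a stated window, and the 8-week assessment is counted from there.
- In Section 7, distinguish stopping stimulation from leaving outcome assessment. Neuropsychological and EEG assessments continue where the investigator judges them safe and the participant still consents. The criteria for stopping stimulation are unchanged.
- In Section 14, state that all randomized participants are analysed as assigned, and add a missing-not-at-random sensitivity analysis.

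The cost is protocol wording, a few assessment visits for early stoppers and a little more analysis work.

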# 5. Sub-Study Procedures:

not applicable

#### 6. Criteria for Inclusion of Subjects:

- Age between 18 and 85
- Female and male subjects
- All races/ethnicities
- Fluent in speaking and reading English

- Capable of understanding and signing an informed (cognitive screening and questions on understanding of the study are included to assess capacity)

- Has had a TBI: loss of consciousness less than 24 hours, posttraumatic amnesia less than 7 days, Glasgow Coma Scale no less than 12 at the time of injury, and Glasgow Outcome Scale-Extended (GOSE) of at least 5 at the time of evaluation.

- Has a subjective complaint of verbal retrieval difficulties evaluated with the following questions. Affirmative answers of yes to two or more of these questions is considered indicative of a subjective verbal retrieval complaint:

a. Do you have trouble finding words when in conversations with others?

b. Do you have difficulty remembering lists of things when these are told to you verbally or if the items are written down?

c. Do you have trouble producing the correct name of an object when referring to it?

d. Do you have difficulty following the conversation of other people because you do not understand what people are saying? Do you have difficulty hearing? (In this case, the answer to the first question

has to be yes and the second no for this question to be considered positive for a verbal retrieval deficit.)

- Has a subjective report of word finding difficulty assessed by the Questionnaire for Word Finding Complaints, that includes 13 Likert-type questions regarding several aspects of word retrieval.

# 7. Criteria for Exclusion of Subjects:

- Lifetime major neurologic syndromes (e.g., stroke, epilepsy, brain tumor)
- Lifetime major cardiovascular conditions (e.g., heart attack, heart failure)
- Current substance use disorder
- Lifetime major psychiatric disorders (e.g., schizophrenia, bipolar disorder)
- Current sensory or physical impairment that interferes with testing
- Implanted device such as a pace maker or other neuro-stimulator
- Has metal fragments in head
- Pregnancy

If a medical condition becomes apparent during the evaluation or follow-up that indicates an increased risk then the subject's involvement in the study will be discontinued.

#### 8. Sources of Research Material:

Research material from questionnaires and interviews will include data about clinical diagnosis, date of birth, sex, race, education level, personal medical history, and contact information including name, address, and telephone number. Neuropsychological testing research material will involve results for word retrieval, episodic memory, processing speed, executive functions, and visuospatial organization that will be for research purposes only. EEG research material will involve (1) latency of the frontal and left fronto-temporal ERPs and (2) magnitude (spectral power) of the frontal theta (4-8 Hz) oscillatory activity, both of which will also be for research purposes only. MRI data will include MPRAGE, T2FLAIR, and DTI images. All data will be stored on password protected computers (digital data) or in a locked cabinet in a secure location (physical data) that is password protected and accessible only to study personnel. Of note, clinical information may be collected from the subjects if they undergo assessments for these in standard clinical care visits at UTSW.

# 9. Recruitment Methods and Consenting Process:

Recruitment for the civilian TBI cohort will primarily be supported by the UTSW memory, TBI, neuropsychology clinics, all following a large population of TBI patients. In addition, we will us several strategies to maximize recruitment. These will include 1) providing study-related information with colleagues at UTSW via e-newsletters and university presentations, 2) placing flyers in exam rooms and waiting areas at UTSW memory/TBI/neuropsychology clinic facilities, and 3) advertising the study on the UTSW website, our lab website and social media using e-flyers.

Prospective participants will undergo telephone screening for conditions in their medical history as well as current medications to save them time and effort from coming to UTSW to enroll in the study if they ultimately will not meet major inclusion/exclusion criteria.

Prospective participants meeting pre-screening inclusion/exclusion criteria (over the telephone) will be scheduled an appointment to review the study procedures and Consent Form. Study staff will go over the consent form in detail with the prospective participant and answer any questions about the procedures. Participants will be asked to sign the Consent Form if they understand the study procedures, appreciate potential risks/benefits, and desire to be involved in the study.

If, at any time, the subject wishes to withdraw from the screening and consent process, they will do so without penalty.

# 10. Potential Risks:

Overall, there is of injury from participating in this research.

#### Risks from the HD-tDCS:

Overall, HD-tDCS has been found to be a safe, well tolerated investigational device as well as a treatment tool when used within the standard parameters. No serious adverse advents caused by HD-tDCS have been reported in the scientific literature. The research team will stop the procedure immediately if the subject chooses. Common side effects include:

- Possible skin sensations, such as tingling, itching, and burning sensations at the site of electrodes, that resolves when stimulation is finished. When experienced, the majority of these are mild in nature with fewer than 4% of individuals describing the sensations as intense.
- Very rarely, temporary skin irritation may occur under the electrode. This creates a darkening of the skin, which normalizes after a week and heals. The size of such is a few millimeters.

To minimize risk, all subjects will be monitored with one-on-one direct supervision during HD-tDCS sessions. If subjects experience discomfort more than the mild tingling or itching expected during HD-tDCS and are unable to continue, the HD-tDCS session will be immediately terminated.

#### Risks from EEG:

- Tiredness
- Emotional discomfort

# Risks from MRI acquisition:

The scanner makes a loud, banging or tapping noise while acquiring images. Participants may experience nervousness from confinement in a tight space (claustrophobia). Participants may experience some discomfort and fatigue from lying still during scanning. There are no known effects from exposure to magnetic fields, unless in the presence of the following: heart pacemaker; heart valve replacement, or aortic clips; metal fragments in their eyes, skin, or elsewhere in their body; brain clips or pieces of metal used in aneurysm surgery or intracranial bypass; venous umbrella; pieces of metal in the body resulting from work as a sheet-metal worker or welder; clips placed in an internal organ; prosthetic devices, such as middle ear, eye, joint, or penile implants o joint replacement; hearing aid that cannot be removed; neurostimulator; insulin pump; intrauterine device (IUD); shunts or stents; metal mesh or coil implants; metal plate, pin, screws, or wires, or any other metal implants

# Risks Pertaining to Loss of Confidentiality and Privacy:

Confidentiality of participants is a priority for research staff and also is presumed and must be maintained unless the investigator obtains the express permission of the subject to do otherwise. Risks from breach of confidentiality include invasion of privacy, as well as social and economic risks. Economic risks include alterations in relationships with others that are to the disadvantage of the subject, and may involve embarrassment, loss of respect of others, labeling with negative consequences, or diminishing the subject's opportunities and status in relation to others. These risks include loss of wages or income, and/or damage to employability or insurability.

